### Sample size

We require a minimum of 342 DMPA clients randomized to receive care from either the LHV or an LHW (1:1 allocation) for 90% power and 5% significance level to test the non-inferiority hypothesis that LHWs can screen potential DMPA clients for method initiation just as adequately as LHVs with a non-inferiority margin of 7.5%, assuming that both LHVs and LHWs perform at a 95% success rate. In Pakistan, there is usually at least one LHV assigned to a health facility and many more LHWs affiliated with and under the supervision of resident LHVs. Therefore, we will use a 3 to 1 ratio of LHWs to LHVs at each health facility in the trial. The three LHWs will be placed on rotation to cover a three-month enrollment and data collection period in the health facility. Rotations among the three LHWs will be based on their individual availability and schedules; not on their perceived competencies or the preference of facility staff.

In order to meet the desired sample size from LHWs and LHVs, we will select 10 health facilities that provide the most DMPA in Karachi and Thatta districts. These facilities will be distributed between rural and urban areas. For logistical reasons, we plan to obtain the full target sample size of 342 DMPA initiators from the urban health facilities to ensure that adequate analyses can be done with this group. We will recruit additional participants from rural facilities to help assess possible differences in performance between LHVs and LHWs in rural and urban areas. Although, we don't expect these differences to exist, the additional sample size will help us to assess whether differences may be likely to exist. If we can be comfortable that providers in rural and urban areas perform in similar manner, the overall sample size for the analysis may be pooled for an increase in power. Please note, however, that the additional sample size from rural areas will not be adequate for separate analyses by location or to assess rural and urban differences statistically. Rural facilities will likely provide a much lower number of DMPA acceptors in the three-month data collection period, but they will each be selected for their ability to enroll at least 20 new acceptors in that period of time. We will then expect to enroll approximately 100 DMPA acceptors from the rural facilities in the recruitment period for an overall total sample size of approximately 442 for this study.

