We require a minimum of 342 DMPA clients randomized to receive care from either the LHV or an LHW (1:1 allocation) for 90% power and 5% significance level to test the non-inferiority hypothesis that LHWs can screen potential DMPA clients for method initiation just as adequately as LHVs with a non-inferiority margin of 7.5%, assuming that both LHVs and LHWs perform at a 95% success rate. In Pakistan, there is usually at least one LHV assigned to a health facility and many more LHWs affiliated with and under the supervision of resident LHVs. Therefore, we will use a 3 to 1 ratio of LHWs to LHVs at each health facility in the trial.

For logistical reasons, we plan to obtain the full target sample size of 342 DMPA initiators from the 5 urban health facilities in Karachi to ensure that adequate analyses can be done with this group. We will recruit additional participants (~100) from 5 rural facilities in Thatta to help assess possible differences in performance between LHV and LHWs in rural and urban areas, but the expectation is that there will be no difference. LHWs undergo standardized training in Pakistan. If we can be comfortable that providers in rural and urban areas perform in similar manner, the overall sample size for the analysis may be pooled for an increase in power. The decision whether to pool the data or not will be made during the blind review of the data as described below.

Given the relationship between LHWs and LHV within clinics, we plan to account for the correlations of participant outcomes within providers and providers within clinics in the analysis. We expect that some of these correlations would lead to decreases in power and others to lead to increases in power for within clinic comparisons. Power calculations were not adjusted for these potential correlations as the net effect on power may be offset with each other.

V. General Analytic Considerations

A. Data Sources

A.1 Client exit interview

Client exit interviews measure the study's secondary outcomes of client satisfaction with the method and provider. The exit interview also provides additional information related to appropriate screening such as discussion of side effects, warning/danger signs, advantages and disadvantages of DMPA use with clients. The client exit interview includes questions on the following domains:

1. Sociodemographic characteristics
2. Experiences using contraceptive methods
3. Factors in her decision to use DMPA

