There are 15 screening questions on the job aid that providers use to determine if a client is or is not a good candidate for DMPA or needs further evaluation before initiating DMPA. The provider makes a global decision of eligibility or ineligibility based on the job aid items and whether or not she would subsequently initiate the client on DMPA. The observer notes the provider's decision whether to start the client on DMPA. This global decision (and not agreement on every screening item), is compared with the gold-standard nurse's assessment of client eligibility to generate the outcome variable for appropriate screening. Thus, the gold standard nurse's overall assessment of eligibility is made after the provider's assessment, and s/he is the final arbiter of eligibility. Thus, if the gold standard nurse determines that the client is eligible to use DMPA, the latter will receive the injectable regardless of the provider's assessment. To avoid bias, the gold standard nurse is blinded to the type of provider who assessed the client beforehand. Whether or not they are deemed eligible to use DMPA as their chosen method, all clients will receive counseling appropriate to their circumstance.

Counseling for DMPA use

Appropriate counseling is a composite binary variable that will be calculated from observations of the discussion between the provider and client. If the provider spoke to the client about side effects, warning or danger signs, advantages, and disadvantages of DMPA, then the conditions are met for appropriate counseling (all conditions must be met for considering the counseling appropriate). If any is missing, the counseling is deemed inappropriate. These variables will also be presented separately in the descriptive analyses by type of provider (and urban/rural setting if the data are not pooled).

Appropriate injection technique

Appropriate injection technique is assessed using checklists for DMPA-IM and DMPA-SC previously developed and validated for this purpose. To meet the criteria for appropriate administration of the injection, the provider must complete 80% of the items on the checklist (i.e., at least 18 out of 22 for SP and at least 14 out of 17 for IM).

D. Blind Data Review

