Even though the study is open labeled, the randomization was prepared by an independent randomization manager and data management is separated from the analysis team. Thus, the analysis team will initially be blinded to the group assignments. Unblinding of the analysis team will follow a three-step process: First, key decisions regarding the primary and secondary outcomes listed above will

be made blinded to study group assignment. These outcome variables will be constructed, checked for missing data, distributional anomalies or other problems, finalized and verified. Decisions about re-categorization, transformation, missing data, and final variable definition will be completed after initial descriptive analysis and prior to further analysis for the specific objectives. Descriptive analysis of the outcomes will be done by facility and rural/urban designation. This check will also include a check of protocol violations, such as randomization errors (this review will be coordinated between the data manager and the randomization manager to maintain blinding of the analysis team) to decide if any data should be excluded from the analysis. Primary analysis will be conducted based on the intent to treat (ITT) approach where all participants randomized will be analyzed in the study group to which they were randomized. During blind review, decisions will be made regarding any modification to the ITT principle for primary analysis and whether a per protocol analysis will be conducted as secondary or sensitivity analysis. Second, once these key decisions have been made, the randomization manager will provide a participant list with blinded study arm assignments to the analysis team. A descriptive bivariate analysis will be done using blinded treatment assignments stratified by rural/urban designation to assess whether pooling the data will be appropriate. A decision whether further analysis will be pooled or not will be done at this time. Partial blinding will be maintained until statistical conclusions regarding the primary outcome (screening outcome) and primary analysis have been made and verified. This will be based on the pooled data or on the urban data only depending on the decision made in the prior step. The analysis team will be fully unblinded for all remaining analysis.

E. Test Size and Confidence Levels

The type I error for the non-inferiority test and other performance outcomes will be set at the two-sided $\alpha=0.05$ significance level.

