VI. Analysis of Fieldwork Data

An analysis of fieldwork data will be presented. This will include the number of DMPA acceptors approached, included, and randomized to LHW or LHV care.

VII. Analysis of participant characteristics

A descriptive summary of DMPA user, LHV, and LHW characteristics will be presented by urban and rural setting. DMPA client characteristics will include age, marital status, education, number of children, desire for more children, and birth spacing plans. Provider characteristics will include age, marital status, education, years of service, and years of DMPA experience.

VIII. Analysis of Study Objectives

We plan to compare a series of indicators of the performance of LHWs compared to LHVs in the provision of injectable contraception services. Our primary outcome, appropriate screening, is a binary variable comprised of the gold standard nurse's assessment of client eligibility for DMPA compared with the LHV's or LHW's assessment of client eligibility. If the LHV's or LHW's assessment agrees with the gold standard nurse's assessment, the screening is deemed appropriate.

Analytical model

We will test the non-inferiority hypothesis that LHWs can screen potential DMPA clients for method initiation just as adequately as LHV with a non-inferiority margin of 7.5%. Given the relationship between LHWs and LHV within clinics, we will employ a generalized mixed model using a logit link to account for the correlations of participant outcomes within providers and providers within clinics. Random effects will be included for clinics and providers within clinic. The non-inferiority test will be conducted at a 5% significance level. A similar approach will be used to compare appropriate counseling. No covariate adjustments are planned for the primary analyses. However, exploratory analyses will include the following covariates: LHV/LHW age, marital status, education level, years of service, years of experience with DMPA, and average DMPA-IM injections given per month prior to the trial. Years of service, years of experience with DMPA, and average injections per month will be analyzed either as categorical or continuous variables based on exploratory analyses; either odds ratios or beta coefficients will be reported.

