Appropriate counseling defined as having discussed side effects, warning/danger signs, advantages, and disadvantages of DMPA				

Table 4: Comparison of Lady Health Workers and Lady Health Visitors on DMPA service delivery indicators (n, %)

	Urban	Rural		
	LHW	LHV	LHW	LHV
Appropriate screening				
Appropriate counseling				
side effects				
danger signs				
advantages/disadvantages				
Appropriate injection technique				
Needle stick injuries				
Client log maintained				

Objective 2: Client Satisfaction and Client-Provider Interaction

Table 5: Exemplar of Client Satisfaction and Client-Provider Interaction items (n, %)

	LHW		LHV	
	SP	IM	SP	IM
Satisfaction with method				
very satisfied				
somewhat satisfied				
not satisfied				
Satisfaction with services				
very satisfied				
somewhat satisfied				
not satisfied				
Satisfaction with provider				
very satisfied				
somewhat satisfied				
not satisfied				
Comfort asking questions				
yes				
no				

Figure 1: Graphic presentation of observation checklist for screening

Observation Checklist to Evaluate Providers Who Screen Clients for Initial DMPA Use

Type of provider being observed: Lady Health Worker
Lady Health Visitor

Please record the response given to the provider by the client for the following items. If the provider does not ask the question, please draw a line through the item.

NO	1. Have you ever been told you have breast cancer?	YES
NO	2. Have you ever had a stroke or heart attack, or do you currently have a blood clot in your legs or lungs?	YES
NO	3. Do you have a serious liver disease or jaundice (yellow skin or eyes)?	YES
NO	4. Have you ever been told you have diabetes (high sugar in your blood)?	YES
NO	5. Have you ever been told you have high blood pressure?	YES
NO	6. Do you have bleeding between menstrual periods, which is unusual for you, or bleeding after intercourse (sex)?	YES
NO	7. Have you ever been told that you have a rheumatic disease such as lupus?	YES
NO	8. Do you have two or more conditions that could increase your chances of a heart attack or stroke, such as smoking, obesity, high blood pressure, or diabetes?	YES
NO	9. Are you currently breastfeeding a baby less than 6 weeks old?	YES

If the client answered NO to *all of questions 1–9*, did the provider tell her she is a good candidate for DMPA?
Yes No
Did provider proceed to questions 10–15?
Yes No

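### Screening is scored only as overall agreement with the nurse, so if few women are ineligible the non-inferiority test cannot tell good screening from clearing everyone

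*SAP*

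**What the plan says.** The primary objective in both documents is whether LHWs can screen and initiate women on DMPA as safely and effectively as LHVs. Screening is the outcome on which the trial is powered.

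SAP V.C (Screening for DMPA use) defines what is scored: "This global decision (and not agreement on every screening item". SAP VIII gives the success rule: "If the LHV's or LHW's assessment agrees with the gold standard nurse's assessment, the screening is deemed appropriate". The comparison is a non-inferiority test with a 7.5-point margin, analysed by a logit mixed model with random effects for clinics and for providers within clinics.

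The planning statement (SAP IV) opens with the size: "We require a minimum of 342 DMPA clients randomized to receive care from either the LHV or an LHW (1:1 allocation". Its operating characteristics are given as "for 90% power and 5% significance level". The expected rates behind it appear in the Protocol's sample-size section: "assuming that both LHVs and LHWs perform at a 95% success rate". Rural recruitment may bring the figure to an "overall total sample size of approximately 442 for this study".

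The observer's form (SAP Figure 1) records more than the outcome uses. It instructs: "If the provider does not ask the question, please draw a line through the item". For screening, however, SAP summary Table 2 and shell Tables 1, 2 and 4 carry only the overall agreement variable. The other observed outcomes get more detail. Counseling components are shown separately, and injection technique is built from 22 (SP) or 17 (IM) checklist items.

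**The concern.** Disagreement with the nurse can go two ways: the provider clears a woman the nurse finds ineligible, or refuses a woman the nurse finds eligible. The first is the error that bears on safety, and it can occur only among ineligible women. Overall agreement pools the two and weights them by how common eligible and ineligible women are among those enrolled. If ineligible women are rare, agreement is driven by eligible women, on whom a provider who asks nothing is always right.

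The result is intended to support a change of policy in Pakistan and of the WHO recommendation on targeted monitoring (Protocol, Introduction). A finding of non-inferiority could be read as evidence that LHWs detect women who should not start DMPA, when the data contain almost no information on that.

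**Working it through.** **Inputs.** From the documents: 342 women at 1:1, so 171 per arm; margin 7.5 points; 95% agreement assumed in both arms; 90% power; 5% level; no allowance for clustering. The sample-size statement does not say whether the level is one- or two-sided. SAP V.E does: "The type I error for the non-inferiority test and other performance outcomes will be set at the two-sided" 0.05 level. Results are therefore given at one-sided 5% and one-sided 2.5%. Assumed, because the documents do not give it: the share π of women the nurse finds ineligible.

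**Step 1: the plan's figure.** Farrington-Manning score formula, one-sided 5%. The restricted estimates under a 7.5-point deficit are 0.8933 (LHW) and 0.9683 (LHV).

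- Null variance term: 0.8933×0.1067 + 0.9683×0.0317 = 0.1261
- Alternative variance term: 2×0.95×0.05 = 0.095
- n per arm = (1.645×√0.1261 + 1.2816×√0.095)² / 0.075² = 170.4, rounded up to 171

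The total is 342, which matches the plan. At one-sided 2.5% the same formula gives 211.6, so 212 per arm and 424 in total.

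**Step 2: score of a provider who clears everyone.** She agrees on every eligible woman and on no ineligible woman, so her agreement is 1 − π while her detection of ineligible women is 0.

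**Step 3: probability that a clear-everyone LHW arm is declared non-inferior.** Exact enumeration of two independent binomials, 171 per arm, score test, shown as one-sided 5% / 2.5%:

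| π assumed | LHVs agree 100% | LHVs agree 95% |
|---|---|---|
| 2% | 98% / 94% | above 99% / above 99% |
| 3% | 86% / 75% | above 99% / 99% |
| 4% | 62% / 47% | 97% / 94% |
| 5% | 37% / 24% | 92% / 84% |
| 7.5% | 5% / 2% | 58% / 43% |
| 10% | below 1% / below 1% | 21% / 13% |

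Check on the method: when the true LHW rate is 87.5% against 95%, exactly at the margin, the rejection rate is 4.9% at one-sided 5%.

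**Step 4: the same in counts.** With 171 per arm and no LHV disagreements, the LHW arm passes with up to 7 (5%) or 6 (2.5%) disagreements, even if every one is a wrongly cleared woman. With 9 LHV disagreements it passes with up to 13 or 12. The expected number of ineligible women per arm is 171×0.02 = 3.4 at 2% and 171×0.05 = 8.6 at 5%.

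**Step 5: a less extreme case.** If π is 5% and LHWs miss half of the ineligible women, their agreement is 1 − 0.05/2 = 97.5%. Against perfect LHVs this arm passes 93%/86% of the time.

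**Step 6: what a direct estimate could show.** If all k ineligible women are detected, the exact 95% lower limit is 0.025^(1/k). For k = 9 it is 66%; for k = 3 it is 29%.

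**The case against.** **The ineligible share is not shown to be low.** This stands. Choosing DMPA is not a medical screen, and the enrolment criteria include none. The checklist diverts women with diabetes, high blood pressure, unusual bleeding or a very young breastfed baby, and adds six pregnancy rule-out questions. At about 10% ineligible the test would usually expose a clear-everyone arm.

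**The 5% row against LHVs at 95% is true by construction.** This also stands. A reader might infer from 92%/84% that the design gives a non-screening arm its planned power. That only restates that two arms with equal true rates of 95% pass at design power, and it requires LHVs to agree no more often than someone who never screens. It is not used as evidence here.

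**Clearing everyone is an extreme scenario.** Providers are certified proficient before seeing clients, each encounter is observed, and staff intercede if problems emerge. The scenario is a stress test of the endpoint, not a prediction about LHWs. Step 5 shows that partial failure also passes.

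**The probabilities are not from the planned model.** Correct. The logit mixed model with clinic and provider effects would shift them, and with LHVs at 100% agreement the odds ratio has no finite estimate. The identity in Step 2 does not depend on the model.

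**Safety rests on five endpoints, and wrong refusals matter too.** Both are true, and they are reasons to keep agreement as primary. But counseling, injection technique, needle-stick injuries and logs do not measure whether ineligible women are found. The nurse's check protects women in the trial without making the endpoint sensitive to absent screening.

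**Conclusion.** The concern holds conditionally. The outcome as defined cannot separate competent screening from indiscriminate clearance when few women are ineligible. On the simple test used here, few means roughly 2 to 3% if LHVs agree perfectly, and more if LHVs themselves disagree with the nurse. The size rests on an assumed ineligible share, independent observations and a risk-difference test.

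A reader might go further and infer that the trial will pass LHWs who do not screen, or that its safety conclusion is void. The documents do not support either. They give no ineligible share, they describe trained and observed providers, and at higher shares the test does discriminate. What they do support is narrower: no planned analysis would show which situation arose, although both decisions and the questions asked are to be recorded.

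A related conflict affects the denominator. Protocol III (Observation of screening and counseling) describes verification after the provider has deemed the woman eligible and counseled her. SAP V.C has the nurse decide whatever the provider concluded. If women the provider refused are not assessed by the nurse, wrong refusals cannot be counted and the primary denominator changes.

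**What to change.** Keep agreement as the primary outcome. In SAP V.C and VIII, summary Table 2 and shell Table 4, pre-specify:

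1. The cross-table of provider decision by nurse decision, by cadre, with the number of nurse-ineligible women in each arm.
2. (a) The proportion cleared among nurse-ineligible women and (b) the proportion refused among nurse-eligible women, each with counts and an exact confidence interval.
3. As description only, the share of applicable screening questions asked, from the observer form. Count only questions due before the checklist's own stopping point, so that a provider who correctly stops at a contraindication is not marked down.
4. A statement that, when the interval for (a) is too wide to be informative, the conclusion is limited to overall agreement and does not extend to detection of ineligible women.

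Reconcile the Protocol and SAP on whether the nurse assesses women the provider refused, because (b) and the primary denominator depend on it.

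The cost is SAP wording and one more table, largely from decisions already recorded; (b) is available only if refused women are assessed. Sample size and primary test are unchanged. The downside is that (a) will be imprecise (Step 6) and the headline claim may need qualifying.

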### III. Methodology

#### *Overview*

This will be a randomized controlled trial conducted in Sindh Province, Pakistan, using quantitative methods. Third-party, independent data collectors will be trained to perform onsite observations of screening and counseling of first-time DMPA clients performed by LHWs and LHV in health facilities. Another health facility provider--blinded to the LHW or LHV who provided the initial screening--will verify client eligibility to use DMPA through their own client interview. If the independent screener deems the client eligible to receive DMPA, then the same provider who earlier screened and counseled her on the method will administer the injectable to her. Clients will also be randomized to receive DMPA IM or SP to prevent selection biases between these groups. However, comparisons between these injection techniques will only be considered exploratory, focusing instead on acceptability of and satisfaction with the method as reported by clients.

Survey interviews with participating LHWs and LHV will be conducted four to six months after trial initiation to obtain their feedback on providing DMPA IM and SP and attitudes towards LHW-initiation of injectables.

The study is limited to participating LHWs, LHV and to their clients who voluntarily and independently accept DMPA as their contraceptive method before study recruitment is initiated.

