This is an open-label study – neither study staff nor participants will be blinded to study treatment arms after the point of randomization. Nonetheless, strict policies will be in place to preserve randomization integrity. Randomization documentation will be stored in a secure location. Data recording, assessment of the primary and secondary study outcomes, and other assessments, such as DMPA eligibility assessment by independent facility staff, will be blinded to treatment arm where possible. The FHI 360 lead statistician and data analysts will perform a blinded review of the data to make final statistical decisions that could affect the comparison of the primary and secondary outcomes before fully unblinding the data for final analyses. Details of the analysis processes will be described in the detailed analysis plan.

Screening, counseling and DMPA administration will all be performed by the same LHW or LHV randomized to provide services to that client. The receipt of DMPA IM or SP is being randomized to avoid an imbalance of DMPA type that could occur if clients are given the choice between the two delivery systems. Similarly, provider bias/preference for one form or the other of DMPA could result in the same. The following graphic describes the procedures, including randomization, to be adopted in this trial.

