## Data collection procedures

### *Observation of screening and counseling*

After the DMPA client has provided informed consent and been randomized to see an LHW or an LHV, the RA posted at the study site will observe the screening and counseling interaction between the LHW/LHV and client. The RA will request that the interaction be conducted in accordance with the health facility's privacy policy and with the normal procedure for client-provider interaction. As such, we are currently unable to specify a range of time in which these observations will be performed.

The RA will first record observations using the first part of the checklist devoted to screening for client eligibility. If the LHW/LHV deems the client eligible for DMPA, then the RA will record whether or not the LHW/LHV proceeded to deliver key counseling elements of DMPA use to the client. All data will be recorded via pen and paper to be later entered into an electronic database.

After the client has been counseled, the clinic staff assigned at that study site to provide support to the trial will verify that the client is indeed eligible to receive DMPA. The staff member will serve as the independent gold standard for LHW and LHV performance. If s/he confirms that the client is eligible for DMPA use, the client will then receive DMPA subcutaneously or via an intramuscular injection from the same LHW or LHV who earlier screened and counseled her. If the staff member determines that the woman is not eligible for DMPA use, she will be offered another method and released from participation in the trial. The LHV/LHW who incorrectly deemed the client eligible for DMPA will not be penalized and the event will be treated and utilized as a learning experience.

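### The gold-standard nurse is masked to who screened the woman but not, in any stated rule, to the eligibility decision that her own assessment is used to score

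*SAP*

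**What the plan says.** The SAP (V.C, Screening for DMPA use, and VIII) scores screening as appropriate when the provider's global decision matches the nurse's. On timing, "the gold standard nurse's overall assessment of eligibility is made after the provider's assessment, and s/he is the final arbiter of eligibility". On masking, "To avoid bias, the gold standard nurse is blinded to the type of provider who assessed the client beforehand".

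The protocol has two masking statements. In the Overview the second assessor is "blinded to the LHW or LHV who provided the initial screening" and "will verify client eligibility to use DMPA through their own client interview". Under Randomization procedures the commitment is softer: "DMPA eligibility assessment by independent facility staff, will be blinded to treatment arm where possible".

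The documents describe the route to the nurse differently:

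- Protocol, Observation of screening and counseling: "If the LHW/LHV deems the client eligible for DMPA, then the RA will record whether or not the LHW/LHV proceeded to deliver key counseling" elements. After counselling, the staff member checks that the woman is in fact eligible. The next sentence begins "If s/he confirms that the client is eligible for DMPA use". If the check fails, the text speaks only of a provider who wrongly cleared her. No path is described for a woman whom the provider turned down.
- SAP V.C: a woman whom the nurse finds eligible receives the injectable whatever the provider concluded, and all clients are counselled whether or not they are found eligible.

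**The concern.** A reference standard should be formed without knowledge of the result that it is used to judge. Here every masking statement concerns who did the screening (person, cadre or arm), and none concerns what was decided. Masking to cadre guards against favouring one cadre. It does not guard against leaning toward the provider's decision in both arms.

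That matters because the outcome is agreement. If the nurse knows or can guess the decision and sometimes goes along with it, disagreements disappear from the data. Where LHWs truly do worse, losing the same share of disagreements in each arm shrinks the measured deficit. In a non-inferiority trial, a shrunken deficit makes a wrong positive conclusion more likely.

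**Working it through.** **Inputs.** 342 women allocated 1:1, so 171 per arm; margin 7.5 points; 95% success assumed in both cadres; 90% power; 5% level (Protocol, Sample size; SAP IV). SAP V.E calls the 5% two-sided, so results are shown at one-sided 5% and one-sided 2.5%. The share of would-be disagreements that the nurse gives up, *a*, is in neither document. It is an assumption, shown over a range.

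**Step 1: reproduce the plan's sample size.** Farrington-Manning non-inferiority formula, per arm:

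n = [(z₁₋α·s₀ + z₀.₉₀·s₁) / 0.075]²

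The rates restricted to a 7.5-point difference are 0.968 and 0.893, so s₀ = √(0.968×0.032 + 0.893×0.107) ≈ 0.355. Also s₁ = √(2×0.95×0.05) = 0.308. At one-sided 5%, n = [(1.645×0.355 + 1.282×0.308)/0.075]² ≈ 170.4, so 171 per arm and 342 in total. This matches. At one-sided 2.5% the same formula gives 424.

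**Step 2: effect of the pull on the measured rates.** If true agreement is p, observed agreement is 1 − (1 − a)(1 − p). With the same *a* in both arms, the observed difference is (1 − a) times the true difference.

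**Step 3: chance of falsely declaring non-inferiority.** Take LHV 95% and LHW 87.5%, so that LHWs are worse by exactly the margin. The probabilities come from full enumeration of two binomials with the Farrington-Manning test, 171 per arm, without clustering.

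| a (assumed) | Observed LHV | Observed LHW | Observed difference (points) | False non-inferiority, one-sided 5% | One-sided 2.5% |
|---|---|---|---|---|---|
| 0 | 95.0% | 87.50% | 7.50 | 4.9% | 2.4% |
| 0.10 | 95.5% | 88.75% | 6.75 | 8.2% | 4.1% |
| 0.20 | 96.0% | 90.00% | 6.00 | 13.2% | 7.0% |
| 0.30 | 96.5% | 91.25% | 5.25 | 20.9% | 11.9% |
| 0.50 | 97.5% | 93.75% | 3.75 | 47.1% | 32.3% |

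If the rural sites are pooled (about 442 in total, 221 per arm), the figure at a = 0.20 and one-sided 5% is 14.5%. A Wald test in place of Farrington-Manning gives the same pattern: 5.6% at a = 0 and 19.6% at a = 0.25, with 171 per arm and one-sided 5%.

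**Step 4: where the effect vanishes or reverses.**

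- Both cadres truly at 95%: the difference stays at (1 − a) × 0 = 0, so it is not biased. Power does rise, because both observed rates move toward 100% (Wald test, one-sided 5%: 93.7% at a = 0, 97.4% at a = 0.25).
- Pull of 10% for LHWs and 30% for LHVs, at the margin: LHV 1 − 0.70×0.05 = 96.5%; LHW 1 − 0.90×0.125 = 88.75%; difference 7.75 points. False non-inferiority at one-sided 5% is 4.2%, so there is no inflation.

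**The case against.** The strongest reply is that the documents never say that the nurse is told the decision or shown the provider's form. The decision is noted by the observer, and no text routes that record to the nurse. She conducts her own interview, is called independent, and has the final say; blinded eligibility assessment is also among the procedures to be piloted. All of this reduces deference, and it stands as mitigation. It does not close the gap: a fresh interview can still be held by someone who knows the answer already given, and the woman herself may have been told the result and can repeat it.

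A reader might also infer that a woman's arrival at the nurse reveals that she was cleared. The protocol's flow invites that reading, but it never expressly limits referral to cleared women. The SAP points the other way: if the nurse can approve a woman whatever the provider concluded, women whom the provider turned down must reach her, and if everyone is counselled, prior counselling reveals nothing. What can be supported is that the decision can be inferred under the protocol's flow, and that the two flows conflict.

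Finally, a reader might infer that the design favours non-inferiority in general. Step 4 shows that it does not. Inflation needs a true LHW deficit and roughly equal pull in both arms. Masking to arm is promised only where possible; if it fails and the nurse defers more to LHVs, the effect can run against LHWs.

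**Conclusion.** The concern holds as a gap in the stated masking, not as a demonstrated bias. Neither document masks the nurse to the decision that she is used to score, and the protocol's flow lets that decision be inferred.

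For an assumed pull of 10% to 30%, equal in both arms, with LHWs truly worse by the margin and 171 per arm, false non-inferiority rises from 4.9% to about 8% to 21% at one-sided 5%, or from 2.4% to about 4% to 12% at one-sided 2.5%. The 50% row is an extreme, because it needs half of all disagreements to be dropped despite a separate interview. The pull cannot be estimated from the documents. The calculation also leaves out clustering and does not use the planned mixed model, so the figures show scale and are not forecasts. The gap should be closed because the trial is meant to inform policy and a WHO recommendation, and closing it is cheap.

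**What to change.** Amend the protocol (Overview; Randomization procedures; Observation of screening and counseling) and SAP V.C to state that:

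1. Every randomised woman goes to the nurse with the same neutral instruction, whatever the provider decided.
2. The provider's decision and the research assistant's checklist are withheld from the nurse.
3. The woman is asked not to disclose what she was told.
4. The nurse records her decision on her own form before anything is revealed.

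Reconcile the protocol and the SAP on which women reach the nurse and which are counselled beforehand. Which clinical flow is right is for the trial team to decide.

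Add one item, completed after the nurse's decision is recorded, on whether she had learned the provider's decision, and report its frequency by arm. Any analysis that leaves out the unmasked cases should be labelled descriptive only, because it selects on an event after randomisation that may be related to the outcome.

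The cost is procedure wording, brief training of research assistants and one tick-box. The sample size does not change and no staff are added. Some disclosure by clients may remain, and the added item would help to show how much.
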